**Comment [CFASTD3]:**  
(in stata Code in italics added 1/9/2007; omission was an oversight.):  

```

gen nocondc=1-(sexfswnocondom==6)
replace nocondc=.a if sexfswnocondom==66
replace nocondc=. if sexfswnocondom=.
replace nocondc=0 if sexfswnum==0 & gender==1
replace nocondc=0 if sexfsw==0 & gender==1
replace nocondc=0 if eversex==0 & gender==1
replace nocondc=. if gender==0 | gender==.

```

Omission in code creating variable caused rates to be dramatically overestimated for interim analysis; those who hadn't had sex w/FSW in last 12 months (but who had previously) were mistakenly assigned 1 rather than 0 (of 1407 assigned 1, these accounted for 941).

Sexmsm	Sex with male	GPS SA Q2.11 (males only)		
Msmnum	How many times sex w/male	GPS SA Q2.14 (males only, but variable "msmnum" received at interim analysis shows everyone responding to this including women and men who did not acknowledge MSM. Looks like not correct data for this question.)	0=None 1-4=? 66=Doesn't remember	
Msmnocond	How many times sex w/male w/o condom	GPS SA Q2.15 (males only, and those who acknowledge MSM.)	1-4=actual #; 5= more than 4; 6=Always uses condom; 66=Doesn't remember	
Nocondm	Noncondom use with male in last 12 months (men only)	Created variable Omission in code creating variable for interim analysis was an oversight and led to overstating rates; see note.	1=yes (had sex with male without condom in last year); 0=no (always used condom or no sex with male)	Outcom
Sexlastpartnum	Number of times sex with last partner in last 3 months	GPS SA Q3.11	1-20=actual # 21=more than 20; 66=doesn't remember	
Sexlastpartnocondom	Number of times sex with last partner in last 3 months without condom	GPS SA Q3.12	1-20=actual # 21=more than 20; 22=always uses condom; 66=doesn't remember	
Nocondl	Noncondom use w/last partner (GPS)	Created variable	1=yes (had sex with last sex partner without condom in last year); 0=no (always used condom or no sex in last 3 months)	Outcom
hlthseek	Health seeking behavior – "If you had abnormal secretion ... what would you do first?"	GPS SA Q2.1	=Nothing =Consult friend =Pharmacy =Doc/Clinic =Hospital =Meds @ home =Other	
Workplace	Workplace type for	FSW questionnaire Q503 (last 7 days)	1=Brothel;	covariate

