**Comment [CFASTD4]:**  
(in stata: Code in italics added 1/9/2007; omission was an oversight):  

```

gen nocondm=1-(msmnocondom==6)
replace nocondm=.a if msmnocondom==66
replace nocondm=. if msmnocondom==.
replace nocondm=0 if msmnum==0 & gender==1
replace nocondm=0 if msm==0 & gender==1
replace nocondm=0 if eversex==0 & gender==1
replace nocondm=. if gender==0 | gender==.

```

Omission for interim analysis was an oversight and led to overstating rates (all MSM got labeled as 1, should not have).

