**Comment [CFASTD5]:**  
(in stata: Code in italics corrected 1/9/2007; omission was an oversight):  

```

gen nocondl=1-(sexlastpartnocondom==22*)
replace nocondl=.a if sexlastpartnocondom==66
replace nocondl=. if sexlastpartnocondom==. /* didn't change variable */
replace nocondl=0 if sexlastpartnum==0
replace nocondl=0 if eversex==0

```

For the interim analysis, I mistakenly assumed that the code for always using condom was 6, as for the 2 previous condom use variables. It should have been 22. Thus 115 people were assigned 0 when they should have been 1 and 1314 were assigned 1 when should have been 0, so nocondom use in last 3 months with last sex partner were overestimated.

	FSW	or Q504 (last month)	2=Nightclub; 3=Bar; 4=Street; Other 99=no response	
Culinter	Condom use w/ last intercourse (FSW)	FSW questionnaire Q618 (is this only among women whose last sex was vaginal intercourse? – Q617?)	1=Yes 2=No (I created ‘cl’, same variable but 0=no/1=yes)	Outcome
	Can read/write?	FSW questionnaire – Q204	1=yes to both 2=can read 3=can write 4=neither	covariate
	Ever married or cohabitant?	FSW questionnaire – Q304	1=yes, 2=no, 99=no response	covariate
	Living with sex partner?	FSW questionnaire – Q309.  For FSW, Will make 0/1 variable (1,2,4=yes, 3 or 5=no)	1=married live w/spouse; 2=married live with other sex ptr 3=married not living with sex ptr 4=not married, cohab; 5 = not married not cohab 99=no response	covariate
	Have dependents?	FSW questionnaire – Q310	1=yes, 2=no, 99=no response	Covariate
	Charged last client	FSW questionnaire – Q616 if last sex partner was client. If second to last sex partner was last client, then Q629. If sex partner before that, then Q643		

\* To aggregate results to the city level the number of positive results in a given city/survey are divided by the number of nonmissing results from that city/survey.

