Sexfswnocondom	How many times sex w/ prostitute w/o condom in last 12 months	GPS SA Q2.10 (males who gave response of 1 or more to 'sexfswnocondom');	1-4=actual #; 5=more than 4; 6=Always uses condom; 66=Doesn't remember	
Nocondc	Noncondom use w/ prostitute in last 12 months (men only):	Created variable Omission in code creating variable for interim analysis caused rates to be dramatically overestimated; See note.	1=yes (had sex with prostitute without condom in last year); 0=no (always used condom or no sex with prostitute)	Outcome

Sexmsm	Sex with male	GPS SA Q2.11 (males only)		
Msmnum	How many times sex w/male	GPS SA Q2.14 (males only, but variable "msmnum" received at interim analysis shows everyone responding to this including women and men who did not acknowledge MSM. Looks like not correct data for this question.)	0=None 1-4=? 66=Doesn't remember	
Msmnocond	How many times sex w/male w/o condom	GPS SA Q2.15 (males only, and those who acknowledge MSM.)	1-4=actual #; 5= more than 4; 6=Always uses condom; 66=Doesn't remember	
Nocondm	Noncondom use with male in last 12 months (men only)	Created variable Omission in code creating variable for interim analysis was an oversight and led to overstating rates; see note.	1=yes (had sex with male without condom in last year); 0=no (always used condom or no sex with male)	Outcome
Sexlastpartnum	Number of times sex with last partner in last 3 months	GPS SA Q3.11	1-20=actual # 21=more than 20; 66=doesn't remember	
Sexlastpartnocondom	Number of times sex with last partner in last 3 months without condom	GPS SA Q3.12	1-20=actual # 21=more than 20; 22=always uses condom; 66=doesn't remember	
Nocondl	Noncondom use w/last partner (GPS)	Created variable	1=yes (had sex with last sex partner without condom in last year); 0=no (always used condom or no sex in last 3 months)	Outcome
hlthseek	Health seeking behavior – "If you had abnormal secretion ... what would you do first?"	GPS SA Q2.1	=Nothing =Consult friend =Pharmacy =Doc/Clinic =Hospital =Meds @ home =Other	
Workplace	Workplace type for	FSW questionnaire Q503 (last 7 days)	1=Brothel;	covariate

	FSW	or Q504 (last month)	2=Nightclub; 3=Bar; 4=Street; Other 99=no response	
Culinter	Condom use w/ last intercourse (FSW)	FSW questionnaire Q618 (is this only among women whose last sex was vaginal intercourse? – Q617?)	1=Yes 2=No (I created 'cl', same variable but 0=no/1=yes)	Outcome

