### Statistical Analysis:

#### Descriptive analyses

The following tables will be presented:

- Baseline general population survey (GPS) process outcomes by city (refusal rate, sample size, % giving blood, urine, swabs)[[name] has done]
- Baseline STI rates (Ct, Gc, Syphilis, HIV, Trich, BV) in the GPS by city [[name] has done]

- 2006 GPS process outcomes by city (refusal rate, sample size, % giving blood, urine, swabs) [[name]]
- 2006 GPS demographics (age, gender, etc) by city [UW]
- 2006 GPS STI rates (Ct, Gc, Syphilis, HIV, Trich, BV) by city [UW]
- 2006 GPS rates of condom use among men with commercial sex partners in the last year, rates of condom use among men with male sex partners in the last year; rates of condom use among men and women with their last partner in the last 3 months; by gender [UW]
- Baseline female sex worker (FSW) survey process outcomes by city (refusal rate, sample size, % giving specimens) [[name] has done]
- Baseline STI rates (Ct, Gc, Syphilis, HIV, Trich, BV) in the FSW survey by city [[name] has done]
- 2006 FSW survey process outcomes by city (refusal rate, sample size, % giving specimens) [[name]]
- 2006 FSW demographics (age, workplace type, etc) by city [UW]
- 2006 FSW survey STI rates (Ct, Gc, Syphilis, HIV, Trich, BV) by city [UW]
- 2006 FSW rates of condom use at the last sexual encounter; by city; by intervention arm [UW]

The following graph will also be presented:

- FSW STI rates (Ct, Gc, Syphilis, HIV, Trich, BV) over time in the interventions cities, pooled [[name]]

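### Condom outcomes default to non-use, and the Nocondm reset for men with male partners relies on an item the plan suspects is faulty and does not require to be checked

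*Supplement*

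**What the plan says.** The Variables table of the latest Data Analysis Plan (the last copy in the supplement) marks three created general-population condom variables as outcomes: Nocondc (sex workers), Nocondm (male partners) and Nocondl (last partner). The Nocondc and Nocondm rows refer to a note. The Nocondl row says only that the variable is created. The notes themselves, with Stata code, are margin comments on the preceding marked-up copy of the plan. No other derivation is given.

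The Nocondm code starts from "gen nocondm=1-(msmnocondom==6", so every value other than 6 begins as 1. It then applies "replace nocondm=.a if msmnocondom==66" and a similar line for system-missing. The resets to zero follow, the first being "replace nocondm=0 if msmnum==0 & gender==1". Further lines set zero for men who report no sex with a male or no sex ever, and remove women.

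The Msmnum row of the latest plan records that, in the interim extract, women and men who had not reported male partners all had answers, and concludes "Looks like not correct data for this question". Its codes 1 to 4 are left as a question mark.

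Nocondl follows the same pattern, starting from "gen nocondl=1-(sexlastpartnocondom==22". Its missing-value line is annotated "replace nocondl=. if sexlastpartnocondom==. /* didn't change variable".

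Nocondl is tested with model M1 (Secondary analysis). Nocondm feeds only a summary, listed under Descriptive analyses as "rates of condom use among men with male sex partners in the last year" and also described in the Protocol Summary, section III.

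**The concern.** Two features of the rule deserve attention.

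First, the companion item that repairs Nocondm is one the plan distrusts. Nothing requires the 2006 field to be checked, replaced or left out. The men whose coding depends on it are those the descriptive table is about.

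Second, coding by exclusion is fragile. If a skipped or declined question is stored as anything other than 66 or system-missing, it becomes unprotected sex unless a later reset catches it. For Nocondl that would affect a tested secondary endpoint. An arm difference in how often people decline could then be read as an arm difference in condom use.

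**Working it through.** **1. What the plan admits about the interim coding.** The Nocondc note says that men with no sex-worker contact in the last year "were mistakenly assigned 1 rather than 0 (of 1407 assigned 1, these accounted for 941".

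- Share of ones that were wrong: 941/1,407 = 66.9%.
- Ones remaining: 1,407 − 941 = 466.
- Overcount: 1,407/466 = 3.0-fold.
- The Nocondl note reports 1,314 people wrongly scored 1 and 115 wrongly scored 0, a net overcount of 1,314 − 115 = 1,199.

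Both errors are recorded as corrected in January 2007. The Nocondm note gives no count.

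**2. Where Msmnum matters.** The Nocondm code, run for men who have ever had sex, gives:

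| Stored answer on unprotected acts | No male partner reported | Male partner reported, Msmnum = 0 | Male partner reported, any other Msmnum |
|---|---|---|---|
| 1 to 5 (a count) | 0 | 0 | 1 |
| 6 (always uses) | 0 | 0 | 0 |
| 66 (does not remember) | 0 | 0 | missing |
| system-missing | 0 | 0 | missing |
| an unlisted value, e.g. 0 | 0 | 0 | 1 |

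Msmnum is irrelevant in the first result column. In the other two it changes every row except the always row. The no-male-partner reset cannot act on these men, and a never-had-sex answer would contradict their own report, so Msmnum is in practice their only reset.

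- A false zero overwrites a valid unprotected count, a 66 or a blank with 0. Overwriting a count understates non-use.
- A false non-zero leaves at 1 a man with no male partner in the last year, if an unlisted value was stored for him. This overstates non-use.

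How often each occurs is not in the documents, so no size can be computed.

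**3. Unlisted values in Nocondc and Nocondl.** Neither uses Msmnum, but both share the default. Two things suggest that non-missing skip values existed at interim:

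- The table routes the question on unprotected sex with sex workers to men reporting at least one act, yet the 941 men without recent contact were scored 1. With the missing-value line in force, system-missing values would have been set to missing.
- The Nocondl missing-value line is said to have changed nothing. In the 2002 survey (Trial Summary, Table 1), never having had sex can be derived as 7,485 − 352 − 6,275 = 858 of 7,133 men (12.0%) and 7,781 − 388 − 5,885 = 1,508 of 7,393 women (20.4%). If similar people in the interim survey had been left system-missing, that line would have changed them.

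Neither is proof. The italics marking the added code are lost in the text, so the Nocondc missing-value line may itself have been part of the correction. The Nocondl comment can be read in other ways.

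**4. Code lists.** The unprotected-acts item behind Nocondl lists 1–20, 21, 22 and 66, with no refusal code and no zero. The Nocondl repair needs a zero on Sexlastpartnum, but the table lists none for that item.

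**The case against.** The strongest reply is that the rule already protects the people the plan names. Men who report no male partners score 0 whatever Msmnum holds. Women are set to missing. This stands, with one condition: the code tests for females coded 0, while the table codes them 2, so the two must be reconciled.

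The Msmnum remark is also worded as a suspicion and concerns the interim extract. Nocondm is not in the inferential list. The handheld questionnaire was programmed to limit missing data (Trial Summary, section 4.1), and the never-had-sex reset in the Nocondl code covers that group. All of this stands and limits the point.

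A reader might infer that the reported rates are wrong. The documents contain no 2006 condom rates, and the rates they call overstated are interim ones with corrected code.

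A reader might also carry the threefold Nocondc error over to Nocondm. Nocondc does not use Msmnum, and no Nocondm count exists.

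Finally, one might try to size a spurious arm difference in Nocondl. If a share u of answers is blank and scored 1, with true non-use q, the shift is u(1 − q). The documents give no 2006 value of u and no arm gap in it. The non-response in Table 1 is for other questions on the 2002 paper form. Nor is binomial sampling error the right yardstick for M1. Borrowing the plan's coefficient of variation of 0.10 (set for infection prevalence) and assuming 50% non-use and 550 people per city, the standard error is √[(2×0.05² + 2×0.25/550)/10] ≈ 2.4 points, against √(2×0.25/5,500) ≈ 1.0 point for sampling alone.

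**Conclusion.** The point holds as a weakness in a stated derivation rule. For men who report male partners, Nocondm depends on an item the plan suspects, whose codes are partly undefined and whose 2006 version nobody is required to verify. The descriptive rate of condom use with male partners can be biased in either direction, by an amount the documents do not allow to be computed.

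For Nocondc and the tested Nocondl, the default to non-use is a hazard: any unlisted stored value not caught by a reset becomes unprotected sex. The documents suggest such values existed at interim but do not show that they affect 2006.

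This rests on the marked-up code being the derivation in use. The latest table points to its notes for Nocondc and Nocondm and offers no alternative for any of the three. The primary endpoint is untouched. The change is worth making because it is nearly free and the default-to-non-use construction needed correction once already.

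**What to change.** In the Nocondl, Nocondc and Nocondm rows, state the rule positively:

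- **1** only for a listed unprotected count: Sexlastpartnocondom 1–21, Sexfswnocondom 1–5, Msmnocond 1–5.
- **0** for the always code (22, 6 and 6 respectively), or for a valid answer that places the person in the plan's own no-sex class.
- **Missing** for everything else: 66, blank, unasked or unlisted.

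Re-extract and validate question 2.14 before Msmnum is used, and define its codes. If it cannot be validated, omit it from Nocondm and report how many men with male partners are left missing. State which value of Sexlastpartnum means no sex, and align the gender codes between table and code. Apply the same code to the 2002, 2005 and 2006 surveys.

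The cost is a few lines of code and plan wording, a rerun of three derived variables, and slightly more missing values. Without Msmnum, men with a past but no recent male partner and no valid answer on unprotected acts would move from 0 to missing. That changes the population of Nocondm, which is why their number should be reported.

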### Statistical Analysis:

#### Descriptive analyses

The following tables will be presented:

- Baseline general population survey (GPS) process outcomes by city (refusal rate, sample size, % giving blood, urine, swabs)[[name] has done]
- Baseline STI rates (Ct, Gc, Syphilis, HIV, Trich, BV) in the GPS by city [[name] has done]

- 2006 GPS process outcomes by city (refusal rate, sample size, % giving blood, urine, swabs) [[name]]
- 2006 GPS demographics (age, gender, etc) by city [UW]
- 2006 GPS STI rates (Ct, Gc, Syphilis, HIV, Trich, BV) by city [UW]
- 2006 GPS rates of condom use among men with commercial sex partners in the last year, rates of condom use among men with male sex partners in the last year; rates of condom use among men and women with their last partner in the last 3 months; by gender [UW]
- Baseline female sex worker (FSW) survey process outcomes by city (refusal rate, sample size, % giving specimens) [[name] has done]
- Baseline STI rates (Ct, Gc, Syphilis, HIV, Trich, BV) in the FSW survey by city [[name] has done]
- 2006 FSW survey process outcomes by city (refusal rate, sample size, % giving specimens) [[name]]
- 2006 FSW demographics (age, workplace type, etc) by city [UW]
- 2006 FSW survey STI rates (Ct, Gc, Syphilis, HIV, Trich, BV) by city [UW]
- 2006 FSW rates of condom use at the last sexual encounter; by city; by intervention arm [UW]

The following graph will also be presented:

- FSW STI rates (Ct, Gc, Syphilis, HIV, Trich, BV) over time in the interventions cities, pooled [[name]]

### Inferential analyses

#### *Primary analysis*

The unit of analysis will be the city (i.e. STI prevalence at the city level). This approach is appropriate since the sample size is approximately the same from city to city. The primary analysis of intervention efficacy will be based on the model

$$d_i^O = b_0 + b_1 d_i^B + \varepsilon_i \quad (M1)$$

where  $d_i^O$  is the difference in the primary STI endpoint (combined gonorrhea, chlamydia, trich in women, and syphilis prevalence) between the intervention and control communities (control – intervention) of the  $i$ 'th pair in the final (2006) outcome survey,  $d_i^B$  is the corresponding difference in the baseline survey and  $\varepsilon_i$  is a random error. The hypothesis of interest is

$$\begin{aligned} \text{Ho: } b_0 &= 0 && \text{(no intervention effect)} \\ \text{Ha: } \beta_0 &\neq 0 && \text{(intervention effect)} \end{aligned} \quad (H1)$$

Note that if  $d_i^B$  was not included in the model, this analysis would be equivalent to a paired t-test. The  $d_i^B$  term is included in the model to control for differences in STI prevalence at baseline (which may occur in spite of the matching).

Least squares regression will be used for model fitting. The standardized test statistic  $\hat{b}_0 / se(\hat{b}_0)$  from this analysis has a t-distribution with 8 degrees of freedom. A p-value will be reported for the hypothesis (H1) and a type I error rate ( $\alpha$ ) of 0.05 (two-tailed) will be used to reject/fail to reject the null hypothesis (H1).

The endpoint in the primary analysis will be **combsti** as measured in the GP.

#### *Secondary analysis*

The analysis outlined above will also be used for the following endpoints:

- **combsti** in FSW
- **Ctresul, ggresul, newsyph, tvresul, HIVresul, BV** in GPS
- **Ctresul, ggresul, newsyph, tvresul, HIVresul, BV** in FSW
- **Nocondl** in GPS
- **Culinter** in FSW

To determine if the intervention is more effective in particular subsets of individuals (i.e. those who prefer to use pharmacies for treatment of STI-related symptoms) we will use an individual level analysis of the 2006 GPS data based on the following model

$$\text{logit}(p_{ij}) = b_0 + b_1 T_i + b_2 B_i + b_3 X_{ij} + b_4 T_i X_{ij} + a_i$$

where  $T_i$  is a 0/1 treatment indicator for city  $i$ ,  $B_i$  is the baseline disease prevalence for city  $i$ ,  $X_{ij}$  is a 0/1 covariate indicating whether subject  $j$  in city  $i$  belongs to the subset of interest (i.e. uses FSW) and  $a_i$  is a random city effect ( $a_i \sim N(0, \sigma^2)$ ). The outcome in this analysis will be **combsti**. In the absence of the interaction term, the  $b_1$  coefficient from this model estimates the overall treatment effect (comparable to  $b_0$  in model H1). With the interaction term in the model, the hypothesis  $H_0: b_4 = 0$  will be used to test if the intervention effect on **combsti** differs across levels of  $X$  (e.g. we might expect  $b_4$  to be positive – intervention more effective – in individuals who prefer to use pharmacies for treatment of STI-related symptoms). A two-sided 0.05 level test will be used.

- To determine if the effectiveness of the intervention differs in individuals who prefer to use pharmacies for STI-related symptoms,  $X_{ij} = \mathbf{hlthseek}$ .
- To determine if the effectiveness of the intervention differs in men who use FSW,  $X_{ij} = \mathbf{sexfsw}$  and the analysis is restricted to men

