Counseling to pharmacy clients with STD: For men with a syndrome suggesting urethritis, women with symptoms of abnormal discharge, and for men and women with symptoms of genital ulcer disease seen in pharmacy settings, we adapted a promising client-centered intervention, pilot-tested a motivational interviewing training program with pharmacy workers in Lima, and developed a training video for STD/HIV prevention. The client-centered counseling primarily assesses the client's actual and perceived risk, reduces barriers to risk reduction, and supports behavior change and promotes partner treatment. These objectives reflect the 4 C's of syndromic management for STD: enhancing compliance; counseling for risk reduction; promoting condoms for high risk sex; and sexual contact referral and treatment. Treatment of vaginal discharge with metronidazole 2 g single dose aimed to cure trichomoniasis, and counseling was reinforced at the pharmacy level. Training pharmacy workers to recognize possible cases of PID and genital ulcer disease was also linked to training the workers to refer such cases for management to the members of the PREVEN Network.

STD symptoms recognition and early health care-seeking campaignJ: This health communication campaign, carried out by the PREVEN team in each of the intervention cities, employed pamphlets, posters, local media, radios and local TV stations, with leaders from the PREVEN network and local authorities involved in the process. The main objectives of the campaign included recognition of urethral discharge as an STD and vaginal discharge as possibly an STD and knowledge of the resources for information (web page, trained pharmacies) and treatment (members of the PREVEN network).

---

J The Health Communication Campaign, on early STD symptom recognition and early healthcare-seeking from appropriate providers, was initiated in 2003 and continued, after a short pause, through August 2005. See Section V. Timeline.

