- 6) Rate of Incomplete Testing. The DSMB noted that the proportion of participants with incomplete laboratory data was higher in the control arm than the intervention arm. The study team was advised to investigate possible reasons for imbalance, which could potentially lead to selection bias, and to consider ways of minimizing this during the final follow-up.
- 7) Trichomoniasis. The DSMB reported their concerns about the validity of the TV data due to outlying values in some cities, very low correlation between baseline and follow-up TV rates, a low matching correlation, and the lack of standardization in this endpoint noted by the study team. Since TV rates were relatively high compared with other STIs, there was concern that *noise* in this endpoint could unduly influence the trial results. The DSMB therefore recommended that the primary endpoint for the trial should be amended by omitting TV from the composite STI variable. Sample size calculations should be rechecked to confirm that the trial is still adequately powered for the amended endpoint, although this is expected to be the case. Despite this recommendation, the DSMB considered that intervention effects on TV were also of intrinsic interest. The study team should investigate whether TV testing could be repeated or confirmed in a central location, using standardized procedures. If so, separate analysis of TV findings could be carried out in addition to analysis of the primary endpoint.
- 8) Matched Analysis. Based on information given in the closed report and the strong matching correlation achieved for the amended primary endpoint, the DSMB recommended that the matched pairs should be retained in the final data analysis.

- 9) Chlamydia. Noting that some women provided urine while some provided vaginal swabs for CT testing, the DSMB recommended that the combined prevalence (based on *either urine or vaginal swab*) be used in the primary analysis. A secondary analysis (in women) should be performed based on vaginal swabs alone, providing take-up rates of swabs were similar in the two treatment arms.

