### **Study Design:**

**Overview:** The study is a community randomized trial of 20 medium sized cities in Peru. The cities were initially paired based on STI prevalence measured in a baseline (pre-intervention) survey. One member of each pair was then randomized to receive the intervention, which consists of two primary components: i) pharmacist education to strengthen syndromic management of STI, and ii) outreach to female sex workers (FSW) using a mobile team. The primary outcome (STI prevalence) will be measured in two cross

sectional surveys - one among FSW and the other in the general population of young adults - in each of the 20 Peruvian cities after the intervention has been in place for approximately 2 years.

**Baseline Surveys:** Baseline surveys of STI prevalence in the general population (18-29 year old men and women), FSW and their clients were conducted in 24 midsize (> 50,000) cities in Peru in 2002 and 2003. These surveys collected both behavioral information and biologic samples.

The general population survey (GPS) used year 2000 census data to randomly select households by cluster sampling (each cluster was an average of 40 households). A random sample of clusters was selected for each city. Then a census was conducted for each household in the selected clusters and a random sample of households with eligible members was selected. Within each selected household, one eligible individual (male or female, aged 18 - 29, living in the city for at least 6 months) was randomly selected.

The FSW/client surveys used time-venue sampling. In each city the study team mapped known locations of FSW. Each day of the week was then divided into x parts and a random sample of time/venues was selected. All (?) sex workers present at the chosen venue at the chosen time were invited to participate in the survey.

**Randomization:** From the 24 cities that took part in the 2002 general population and 2003 FSW and client surveys, twenty were selected to participate in the CRT. Matching was employed to reduce imbalances in the randomization. Matching was based primarily on total STI prevalence (chlamydia, trichomoniasis, syphilis, gonorrhea, HIV) in the baseline general population survey. Population size and location (coastal, highland, jungle) were used as secondary matching criteria. Ten cities (one member of each matched pair) were then randomized to receive the intervention. Table 2 shows the matched pairs.

[figure not shown]

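### The subgroup interaction test assumes the subgroup effect is identical in every city; if it varies, the nominal 5% level is exceeded, and the pharmacy-preference subgroup is itself measured after the intervention.

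*Supplement*

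**What the plan says.** In the latest Data Analysis Plan (the version whose composite is combsti), Secondary analysis, the subgroup questions leave the pair-level model M1: "we will use an individual level analysis of the 2006 GPS data based on the following model". The model is

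logit(p_ij) = b0 + b1·T_i + b2·B_i + b3·X_ij + b4·T_i·X_ij + a_i

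Here B_i "is the baseline disease prevalence for city" i, and a_i "is a random city effect", the only random term. X is either hlthseek (would go first to a pharmacy for an abnormal secretion) or, in men only, sexfsw. The hypothesis b4 = 0 is tested for each: "A two-sided 0.05 level test will be used". No reference distribution or degrees of freedom are given.

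The Study Design section of the plan says "Ten cities (one member of each matched pair) were then randomized to receive the intervention". It also says "Matching was based primarily on total STI prevalence". Both subgroup questions are named secondary aims. By contrast, the primary analysis uses 10 pair differences and a t-distribution on 8 df.

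**The concern.** X varies between people within a city, but T does not. b4 compares the X effect in 10 intervention cities with the X effect in 10 control cities. If the X effect differs from city to city for reasons unrelated to treatment, that variation belongs in the standard error of b4. A random intercept captures differences between cities in overall prevalence, not differences in the X effect. The model therefore treats X effects from 20 cities as one common effect measured on thousands of individuals.

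Heterogeneity is plausible here. The protocol describes the cities as coastal, Andean or jungle, dispersed and relatively isolated. The pharmacy component reached only providers who agreed to take part, so what a pharmacy user received may differ by city.

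A second problem concerns hlthseek alone. It is answered in the 2006 survey, after a campaign whose aims included "knowledge of the resources for information (web page, trained pharmacies) and treatment (members of the PREVEN network"). The April 2006 trial summary, section 2.1, adds that people were told to look for the network's sign in pharmacies. The answer may therefore be an effect of the intervention, and the pharmacy group may hold different kinds of people in the two arms.

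At stake is a claim about whom the pharmacy component helps, which could arise with no true effect modification.

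**Working it through.** **Inputs from the documents.** 20 cities in 10 pairs; two-sided 0.05; 500 survey results per city (power table), hence about 250 men; 22% of men with recent sex-worker contact (trial summary, section 3), used as a proxy for sexfsw; male chlamydia 4.0% and gonorrhoea 0.3% (section 1.1); any-STD prevalence 10% (power table).

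**Assumptions.** SD of the city-level X effect (tau) from 0 to 0.5 on the log-odds scale; pharmacy subgroup 30% or 35%; log OR of X equal to 0.4 where the planned model was fitted.

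**Step 1, closed form.** Let s be the sampling variance of one city's log OR for X. With 10 cities per arm the model's variance of b4 is about 2s/10, and the true variance is 2(s + tau²)/10. The real level of a nominal 5% test is then 2·[1 − Φ(1.96/√(1 + tau²/s))].

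- Whole survey, 150 people with X=1 at 12.6% and 350 with X=0 at 8.8% (average about 10%): s = 1/(150×.126×.874) + 1/(350×.088×.912) = .0605 + .0356 = .0961. At tau .2, √(1 + .04/.0961) = 1.19 and 1.96/1.19 = 1.65, giving a level of 10.0%.
- Men, 55 users at 6.0% and 195 others at 4.1% (average about 4.5%): s = 1/(55×.060×.940) + 1/(195×.041×.959) = .322 + .130 = .453. At tau .2, √(1 + .04/.453) = 1.04 and 1.96/1.043 = 1.88, giving a level of 6.0%.

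**Step 2, simulation with true b4 = 0.** Simulation A: 8,000 trials per SD, 500 per city, 35% with X=1, prevalence 10%, fixed-slope Wald test. Simulation B: the planned random-intercept model fitted by maximum likelihood, Wald test, 2,000 trials per setting (Monte Carlo SE about 0.5 points), 30% with X=1 in the whole survey.

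| tau | Whole survey, formula | Whole survey, A | Whole survey, B | Men, formula | Men, B |
|---|---|---|---|---|---|
| 0 | 5.0% | 4.2% | 5.0% | 5.0% | 5.6% |
| .1 | 6.2% | 5.6% | 7.2% | 5.3% | 4.6% |
| .2 | 10.0% | 9.2% | 10.5% | 6.0% | 6.3% |
| .3 | 15.9% | 15.3% | 15.6% | 7.3% | 7.3% |
| .4 | 23.0% | 23.2% | – | 9.2% | – |
| .5 | 30.2% | – | 30.9% | 11.6% | 13.4% |

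The tau = 0 row reproduces the plan's nominal level. A 1,000-trial check with a higher male prevalence (average about 6.6%) gave 6.6%, 9.4% and 16.3% at tau .2, .3 and .5, so the result for men depends on prevalence.

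**Step 3, are the missing pairs the cause?** With tau = 0 and the pair SD on the logit scale raised from 0.2 to 0.5, the planned test rejected 5.6% (men) and 6.1% (whole survey) in 2,000 trials, and 5.1% and 5.1% in 1,000. There is no material inflation.

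**Step 4, city-level alternative.** A paired t on the 10 within-pair differences of city log ORs (9 df) rejected 4.6-5.2% in A and 4.1-5.8% in B. Simulation B added a half to each cell.

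**Step 5, composition of the pharmacy group.** Suppose no effect on anyone's infection, and a control arm with 30% pharmacy users at 12% and 70% others at 9%. In the intervention arm, 10% of people, with 6% prevalence, move from other to pharmacy. Pharmacy becomes (.30×.12 + .10×.06)/.40 = .105, and other becomes (.70×.09 − .10×.06)/.60 = .095. The log interaction is logit(.105) − logit(.12) − [logit(.095) − logit(.09)] = −.21, an OR of .81. These inputs are illustrative. Moving 5% instead gives .89. Moving 10% whose prevalence is 9% gives .93, and 12% gives 1.06. Size and direction depend on who moves.

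**The case against.** **The inflation is conditional.** This stands. At tau = 0 the planned test holds its level. The only between-city variation the documents quantify is a coefficient of variation of .10 for prevalence, about .10/.90 = .11 on the logit scale at 10% prevalence. An SD of .2 to .3 for the X effect is two to three times that. It is possible, but the documents do not support any particular value.

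**The missing pair term.** A reader might infer that dropping the pairs inflates the test, because randomisation was within pairs and "the DSMB recommended that the matched pairs should be retained in the final data analysis". The documents do not support that. b4 is a contrast of within-city effects, so a prevalence level shared by a pair is absorbed by a_i; B_i also carries much the same information as the main matching variable. The board's advice rested on the matching correlation for the primary endpoint as then amended, and the pairs are kept in M1. Nothing in that advice addresses interaction tests.

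**The reference distribution.** The plan states none. The normal reference in the calculations is an assumption about how the model would be run; the gap in the plan is that no degrees of freedom are named.

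**Pharmacy preference.** The quoted aim names pharmacies as a source of information and network members for treatment, and the campaign ended in August 2005. A shift in who answers pharmacy is therefore plausible but not shown. Against that, network members include pharmacies, and the network ran on through 2006.

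**A log OR per city is fragile for sexfsw.** This stands too. With 55 users at 4.5%, about 2.5 cases are expected and P(none) = .955^55 = 8%. The chance that at least one of 20 cities has none is 1 − .92^20, about 81%; at 6% prevalence it is about 49%.

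**Conclusion.** The point holds in a conditional form. The planned test rests on an unstated and unjustified assumption that the X effect is constant across cities. If that fails, the real level for the whole-survey pharmacy test is about 6-7% at an SD of .1, 9-10% at .2 and 15% at .3. For the test in men it is about 5%, 6% and 7%, somewhat more if male prevalence is higher than about 4.5%. The SDs and the pharmacy share are assumptions. The documents do not support saying that the test is anticonservative whatever the data, or that the absent pair term makes it so.

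The measurement of hlthseek after the intervention is a separate, plausible bias of unknown size and direction, and a random slope would not remove it. The primary analysis and the secondary endpoints analysed with M1 are not affected. The change is worth making because both questions are named aims with formal 0.05 tests.

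**What to change.** Either of two changes to the subgroup section deals with the level of the test:

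1. Add a random city slope for X to the model and test b4 with small-sample degrees of freedom based on the number of cities.
2. In each city take combsti prevalence at X=1 minus X=0, form the 10 within-pair control-minus-intervention values, and test their mean with t on 9 df. The risk difference avoids the zero cells that a log OR would meet in the sexfsw analysis.

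For hlthseek, also tabulate the answers by arm, and treat the pharmacy-user result as descriptive if the distributions differ.

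The cost is SAP wording and simple code, plus some loss of power if the X effect truly is constant. The second option also moves the question to the additive scale: an intervention with the same odds ratio in both subgroups can still give unequal risk differences, so the plan should name the scale on which effect modification is claimed. The simulated pair-level test used log ORs; the risk-difference version has the same structure of 10 pair values but was not simulated, nor was the random-slope model fitted.
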